#### 8 SAFETY MONITORING

#### 8.1 Definitions

Adverse event (AE) - An AE is any untoward medical occurrence associated with the use of a drug in humans whether or not it is considered drug-related. An AE can be any unfavorable and unintended sign (e.g., a clinically significant abnormal laboratory finding), symptom, or disease temporally associated with the use of the drug and does not imply any judgement about causality. An AE can arise with any use of the drug (e.g., off-label use, use in combination with another drug and with any route of administration, formulation, or dose including an overdose). Events that are related to the disease under study, COVID-19, should not be considered or recorded as AEs unless the event fits the definition for a serious adverse event (SAE), in which case the SAE must be reported to the electronic data capture (EDC) system for safety reporting purposes in the appropriate time frame.

Laboratory abnormalities should not be recorded as AEs or SAEs unless they are associated with clinical signs or symptoms or require medical intervention. However, each laboratory abnormality (e.g., clinically significant changes detected on hematology, chemistry, or coagulation test) independent from any underlying medical condition that requires medical or surgical intervention, or that leads to interruption of study drug administration or discontinuation, must be recorded as an AE or SAE, if applicable. If the laboratory abnormality is part of a clinical condition or syndrome, it should be recorded as the syndrome or diagnosis rather than as the individual laboratory abnormality. In addition, laboratory abnormalities or other abnormal test assessments that are associated with signs or symptoms that are not part of a clinical condition or syndrome must be recorded as AEs or SAEs if they meet the definition of an AE or SAE.

**Serious adverse event (SAE)** - An event is considered "serious" if, in the view of either the investigator or Sponsor, it results in any of the following outcomes:

- Death
- A life-threatening AE (An event is considered "life-threatening" if, in the view of either the investigator or Sponsor, its occurrence places the patient or participant at immediate risk of death. It does not include an AE or suspected adverse reaction (AR) that, had it occurred in a more severe form, might have caused death.)
- Inpatient hospitalization or prolongation of existing hospitalization
- A persistent or significant incapacity or substantial disruption of the ability to conduct normal life functions
- A congenital anomaly/birth defect
- Important medical events that may not result in death, be life-threatening, or require hospitalization may be considered serious when, based upon appropriate medical judgment, they may jeopardize the patient or participant and may require medical or surgical intervention to prevent one of the outcomes listed in this definition. Examples of such medical events include allergic bronchospasm requiring intensive treatment in an emergency room or at home, blood dyscrasias or convulsions that do not result in inpatient hospitalization, or the development of drug dependency or drug abuse.

**Treatment-emergent** – All AEs will be collected from the signing of informed consent until the EOS visit/Day 60. Non-treatment-emergent AEs are defined from the signing of informed consent to randomization. Treatment-emergent AEs (TEAEs) are defined from randomization through Day 28.

Causality or relatedness - A treatment-related AE (TEAE) is defined as any new AE that begins or any preexisting condition that worsens in severity, after informed consent until the EOS visit (i.e., Day 60+2) and is considered by the investigator to be related to ANA001. All AEs and SAEs should have attribution recorded as treatment- or not treatment-related, in the judgment of the site investigator.

- Related: There is a temporal relationship between the study drug and event, and the AE is known to occur with the study drug or there is a reasonable possibility that the study drug caused the AR. Reasonable possibility means that there is evidence to suggest a causal relationship between the study drug and the AE.
- Not related: There is not a reasonable possibility that the administration of the study drug caused the event, there is no temporal relationship between the study drug and event onset, or an alternate etiology has been established.

**Adverse reaction -** An AR is any AE caused by a drug.

**Suspected adverse reaction (SAR)** - An SAR is any AE for which there is a reasonable possibility that the drug caused the AE. For the purposes of the IND safety reporting, "reasonable possibility" means there is evidence to suggest a causal relationship between the drug and the AE. SAR implies a lesser degree of certainty about causality than AR.

**Unexpected** event- An event is considered unexpected if it is not listed in the Investigator's Brochure (IB), is not listed at the specificity or severity that has been observed, or, if an IB is not required or available, is not consistent with the risk information described in the General Investigational Plan or elsewhere in the IND. Unexpected also refers to events that are mentioned in the IB as occurring with a class of drugs or as anticipated from the pharmacological properties of the drug but are not specifically mentioned as occurring with the particular drug under investigation.

**Severity or intensity** - All AEs that are recorded must have their severity graded. To grade AEs, study sites should refer to the Common Terminology Criteria for Adverse Events (CTCAE v5) criteria (USDHHS 2017:

https://ctep.cancer.gov/protocoldevelopment/electronic\_applications/docs/CTCAE\_v5\_Quick Reference 5x7.pdf).

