#### **8.2.1** Time Frame for Collection

AEs will be collected from the signing of informed consent through study completion (EOS visit; Day 60+2) or study withdrawal.

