#### 9.3.6.1 Treatment-Emergent Adverse Events

All adverse events reported during the study will be coded using a MedDRA (v21.1) dictionary. Non-treatment-emergent AEs will be captured on the appropriate eCRF and a listing will be generated for the randomized set. Only treatment-emergent AEs (TEAEs) will be summarized in the planned safety analyses. The incidence of treatment-emergent adverse events will be summarized by treatment group and the following:

Preferred term

System organ class and preferred term

System organ class, preferred term and severity

These summaries will be presented for the following subsets:

All adverse events

Serious adverse events

Drug-related adverse events

Adverse events leading to study treatment discontinuation.

For tables reporting adverse events by severity, if a subject has multiple occurrences of an adverse event with the same organ class and preferred term, the most severe event will be presented.

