6. ANALYTIC DEFINITIONS

Baseline Measurements will be the last measurement for the corresponding endpoint prior to the first dose of study drug.

Age at Baseline is the last non-missing age collected before the first dose of study drug.

Body Mass Index is calculated as (Weight in kg / (Height in meter)²). The last non-missing weight and height collected before the first dose of study treatment will be used to calculate the baseline body mass index.

Study Drug Exposure is calculated as number of days from first dose day to last. That is:

Study Drug Exposure = Last Study Drug Date – First Study Drug Date + 1.

Study Drug Compliance (%) for a participant is calculated as: 100*total number of doses taken/total number of doses the participant was supposed to have taken during the treatment period. That is, 100*total number of doses taken ÷ (8* Study Drug Exposure [in Days]).

A Treatment-Emergent Adverse Event (TEAE) is any adverse event that occurs on or after first dosing and up through Day 28.

COVID-19 Rescue Treatments that are defined as any treatment approved under NDA or Emergency Use Authorization (EUA) for COVID-19 or off label medications given as direct treatment of COVID-19.

Concomitant Medication will be defined as the medications used on/after the first dose of study drug or started before first dose of study drug and continued during the study.

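### Adverse events with onset on Days 29 to 60 are collected but have no specified by-arm summary or listing, and no all-deaths analysis to Day 60 is specified

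*Protocol*

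**What the plan says.** **Collection.** Protocol 8.2.1: "AEs will be collected from the signing of informed consent through study completion (EOS visit; Day 60+2) or study withdrawal".

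**Classes.** Protocol 8.1 names two. For the first, "Non-treatment-emergent AEs are defined from the signing of informed consent to randomization". For the second, "Treatment-emergent AEs (TEAEs) are defined from randomization through Day 28". SAP section 6, for Part 1, defines a TEAE as "any adverse event that occurs on or after first dosing and up through Day 28".

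**Reporting.** Protocol 9.3.6.1: "Only treatment-emergent AEs (TEAEs) will be summarized in the planned safety analyses". The one AE listing it names is for the other class: "Non-treatment-emergent AEs will be captured on the appropriate eCRF and a listing will be generated for the randomized set". SAP 7.6.1 tabulates TEAE incidence. Its tables of serious, drug-related and fatal AEs are subsets of that incidence.

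**Endpoints.** Protocol Tables 2 and 3 put safety among the primary objectives of both parts. In the endpoint line, SAEs are limited to treatment-emergent ones and deaths are not. Protocol 9.3.6 promises a summary, in the Safety Set, of every safety endpoint. SAP 4.3 lists AEs leading to death but not deaths as such.

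**A second use of the label.** The causality paragraph of Protocol 8.1 attaches the abbreviation TEAE to treatment-related events that arise or worsen "after informed consent until the EOS visit (i.e., Day 60+2) and is considered by the investigator to be related to ANA001".

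**The concern.** The collection window is longer than the reporting window, and the class that should take what is left over stops at randomization. If the reporting rule is followed as written, SAEs and fatal AEs that begin in the second month are recorded by the sites and then drop out of the comparison between arms.

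Safety and tolerability is the only primary objective of Part 1 and one of the primary objectives of Part 2. COVID-19-related events are recorded as AEs only when serious (Protocol 8.1). Sites ask about readmission at telemedicine visits (Protocol 6.3.2), and a readmission meets the SAE definition as an inpatient hospitalization. A readmission for an event with onset after Day 28 would therefore be a collected SAE without a specified table.

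For deaths the problem is different: a primary endpoint without a time limit has no analysis that covers the planned follow-up. Deciding how to show late deaths after unblinding would be a post hoc choice.

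**Working it through.** The plan states no figure on this point that could be reproduced. The check compares windows and then counts days and participants.

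**1. Follow an AE by its onset.**

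| Onset | Class | Protocol 9.3.6.1 | SAP 7.6.1 (Part 1) |
|---|---|---|---|
| Consent to randomization | Non-treatment-emergent | Listing | None stated |
| Randomization to first dose | TEAE in Protocol 8.1, not in SAP 6 | By-arm tables | None stated |
| First dose to Day 28 | TEAE in both | By-arm tables | By-arm tables |
| Day 29 to Day 60 (+2) | Neither class | None | None stated |

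The last row is the gap. The second row shows a separate mismatch: the TEAE window opens at randomization in the protocol and at first dose in the SAP.

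**2. Look for late deaths elsewhere in the specified analyses.**
- SAP 7.4 uses death only as a censoring event for time to discharge.
- No secondary or exploratory efficacy endpoint in either part is mortality.
- The disposition tables (Protocol 9.3.1, SAP 7.1) give reasons for leaving the study and may show some deaths there. The text does not say that death is a category.
- The thromboembolic endpoint stops at 15 days (SAP 7.5.9). The Day 28 limit does not affect it, and it covers nothing later.

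**3. Set the two protocol reporting rules side by side.** Protocol 9.3.6 promises that all safety endpoints are summarized, which includes deaths. Protocol 9.3.6.1 restricts the planned safety analyses to TEAEs. A fatal AE with onset after Day 28 satisfies the first rule and fails the second. The text does not say which prevails.

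**4. Count the days.** 60 − 28 = 32, and 32/60 = 53%. With the +2 window, 62 − 28 = 34, and 34/62 = 55%. These are shares of calendar time, not of events.

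**5. Effect per participant.** This takes the planned arm sizes and a participant whose first SAE or fatal AE begins after Day 28.
- Part 1: 1/30 = 3.3 percentage points of that arm's incidence.
- Part 2: 1/188 = 0.5 percentage points.

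**6. Illustrative range.** The documents give no late event rate. Suppose that a proportion p of participants have a first SAE with onset on Days 29 to 60. The expected number left out is N × p.

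| Assumed p | Part 1, N = 60 | Part 2, N = 376 |
|---|---|---|
| 1% | 0.6 | 3.8 |
| 2% | 1.2 | 7.5 |
| 5% | 3.0 | 18.8 |

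The values of p are assumptions that show scale only.

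**The case against.** A reader might infer that every death or SAE on Days 29 to 60 is missing from the safety tables. The documents do not support that, for three reasons.

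- **TEAE status turns on when the AE occurs.** A death on Day 40 from an AE that began by Day 28 would still enter the SAP's fatal-AE table. Only fatal AEs with later onset escape.
- **Deaths are not explicitly excluded.** They are an unrestricted primary safety endpoint, and Protocol 9.3.6 says that safety endpoints will be summarized. The fault is an unspecified analysis and two rules that disagree.
- **Not all the planning documents are here.** SAP section 1 places the Part 1 tables and listings in a separate document. The SAP covers Part 1 only and was written to protocol Version 4.0. Protocol section 9 gives key details and promises a complete SAP for each part. For Part 2 the point rests on the protocol text alone.

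It can also be said that the Day 28 limit on SAEs is deliberate, since the endpoint itself reads as treatment-emergent SAEs. A Day 28 TEAE window after seven days of dosing is a legitimate choice. It does not explain why later AEs are collected and then given no output at all.

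Late events are not lost to oversight. SAEs are reported within 24 hours and followed through the follow-up period (Protocol 8.3 and 8.4), the DMC sees unblinded data (11.1), and the WHO scale, on which 8 is death, is recorded at Day 60. None of this is a by-arm safety table in the study report.

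The second TEAE label in Protocol 8.1 may be a slip, because the abbreviation list and 9.3.6.1 both use the term for treatment-emergent. It still leaves a related event on Day 40 inside one definition and outside the other.

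**Conclusion.** The point holds in limited form. Under the stated rules, AEs, SAEs and fatal AEs with onset on Days 29 to 60 (+2) have no specified summary or listing. No all-deaths analysis to Day 60 is specified although deaths are a primary safety endpoint. If such events occur, the planned tables would understate their incidence by arm.

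The size is unknown without a late event rate. The per-participant steps (3.3 points in Part 1, 0.5 in Part 2) assume full planned arms and a participant with no earlier event of the same kind. It would be wrong to read the 53% of calendar days as a share of lost safety information: dosing lasts 7 days, the sample-size section assumes median improvement at 11 to 15 days, and risk need not be even over 60 days. Nor do the documents show that mortality will be understated. That depends on whether fatal AEs begin after Day 28 and on what the unseen table shells contain.

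The gap is plain for the protocol text and the Part 1 SAP, and less certain for Part 2. It should be corrected, but it does not undermine the design.

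**What to change.** 1. Keep the Day 28 TEAE tables as they are.
2. Add to Protocol 9.3.6.1 and SAP 7.6.1 two by-arm tables in the Safety Set: all-cause deaths, and all SAEs, each from first dose to Day 60 (+2).
3. Add a listing of AEs with onset after Day 28.
4. Amend the sentence in Protocol 9.3.6.1 that confines summaries to TEAEs, so that it agrees with 9.3.6 and with the new outputs.
5. Remove the TEAE abbreviation from the treatment-related definition in Protocol 8.1.
6. Choose one start point for the TEAE window, randomization or first dose, and use it in both Protocol 8.1 and SAP section 6.
7. Carry the same wording into the Part 2 SAP.

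The cost is some wording, two tables and one listing, all from data already collected. Sample size, power and type I error do not change. The outputs should be specified before unblinding.

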#### **8.2** Documenting Adverse Events

AEs will be recorded in the appropriate electronic case report form (eCRF).

#### **8.2.1** Time Frame for Collection

AEs will be collected from the signing of informed consent through study completion (EOS visit; Day 60+2) or study withdrawal.

#### **8.3** Recording Adverse Events

Whenever possible, diagnoses should be given when signs and symptoms are due to a common etiology (e.g., dizziness, light-headedness, and fall should be reported as "syncopal episode"). Investigators must record their opinion concerning the relationship of the (S)AE to the study drug and record a severity grade (using the criteria defined in the CTCAE v5 [USDHHS 2017:

https://ctep.cancer.gov/protocoldevelopment/electronic\_applications/docs/CTCAE\_v5\_Quick \_Reference\_5x7.pdf]) on the appropriate eCRF. All measures required for (S)AE management must be recorded in the source documents and reported according to the Sponsor's instructions.

All (S)AEs occurring at any time during the study (including the follow-up period) must be followed by the Investigator until resolution, return to baseline, or until the event is deemed stable or irreversible.

#### 8.4 Communicating an SAE/SUSAR to the Sponsor and/or CRO

As soon as a clinical site investigator or other staff member becomes aware of a possible SAE in a study participant, regardless of attributability to study treatment, he/she should enter the AE/SAE information into the EDC system and reported on the SAE report within 24 hours of awareness for reporting to the Sponsor/CRO. The Medical Monitor will review and assess the SAE for regulatory reporting and potential impact on study participant safety and protocol conduct.

# 8.5 Expedited Reporting of SAE/SUSAR to IEC/IRB and Regulatory Authorities

With documentation support from the CRO and Sponsor, US Investigators must promptly submit all expedited safety reports to their IRB/EC within 7 days for fatal and life-threatening events and 15 days for other reportable events. The Sponsor or designee will be responsible for reporting an SAE/suspected unexpected serious adverse reaction (SUSAR) to regulatory authorities.

The FDA will be notified for any subject who is withdrawn from the study for safety reasons and for any DMC decision to pause enrollment or terminate the study.

#### 8.6 Adverse Events of Special Interest

There are no identified AEs of special interest for ANA001.

#### 8.7 Clinical Laboratory Findings

An AE can include any unfavorable and unintended abnormal laboratory findings temporally associated with the use of an investigational product whether or not considered related to the product.

Safety laboratory testing will be conducted as outlined in Section 9.3.6.2 and Appendix 5

#### 8.8 Pregnancy

Pregnancies occurring in participants enrolled in this study must be reported and followed to outcome on the Pregnancy Notification Form. Pregnancy alone is not regarded as an AE unless there is a possibility that ANA001 may have interfered with the effectiveness of a contraceptive medication. Elective abortions without complications should not be considered AEs unless they were therapeutic abortions. Hospitalization for normal delivery of a healthy newborn should not be considered an SAE. Pregnancy is not considered an SAE unless there is an associated serious outcome. Spontaneous abortions should always be reported as SAEs.

#### 8.9 Overdose or Misuse

ANA001 overdose, including misuse or abuse of the product and medication errors, must be reported in the Investigator's notes and captured on the appropriate eCRF(s).

#### 9 DATA ANALYSIS AND STATISTICAL METHODS

In this section, key details of the statistical analyses to be performed using data captured according to this protocol will be provided. This study consists of 2 main parts:

Study Part 1 is designed to primarily assess the safety and tolerability of ANA001 1,000 mg PO BID and

Study Part 2 is designed to primarily assess efficacy of ANA001 1,000 mg PO BID.

A complete statistical analysis plan (SAP) describing all planned analyses for each part will be finalized prior to unblinding of Study Part 1 (database freeze) and database lock after completion of Study Part 2. A DMC charter and DMC SAP will be finalized prior to initiation of Study Part 1.

#### 9.1 Determination of Sample Size

#### **9.1.1 Study Part 1**

60 participants (30 randomized to ANA001 and 30 to placebo) are anticipated to provide sufficient data to assess safety and tolerability of ANA001 in patients with moderate and severe COVID-19. The sample size is based on clinical consideration and is consistent with the size of other studies with similar objectives.

#### **9.1.2** Study Part 2

One study reported that subjects treated with placebo will have a median time to clinical improvement around 15 days (Beigel *et al.*, 2020). Treatment with ANA001 is expected to reduce median time to clinical improvement to 11 days. At least 374 recoveries must be achieved for a log rank test to have 85% power at a two-sided significance level of 0.05.

Assuming a 6 months accrual period and the last enrolled subject will be followed for 30 days, at least 376 subjects must be randomized in 1:1 ratio. That is, at least 188 subjects must be randomized to be treated with ANA001 and 188 subjects to be treated with placebo.

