### 1 SYNOPSIS

Title	A Phase 2/3 Randomized and Placebo-Controlled Study of ANA001 in the Treatment of Moderate and Severe COVID-19 Patients
Phase	2/3
Study Design	This is a randomized, double blind, placebo-controlled multicenter study to investigate the safety and efficacy of ANA001 in the treatment of subjects with moderate and severe coronavirus disease 2019 (COVID-19). A total of 436 subjects who meet all eligibility criteria at Screening will be randomized to be treated with ANA001 1,000 mg twice daily (BID) or matching placebo administered orally (PO). Randomization will be stratified by oxygenation (SpO 2 >93 and <98% on room air versus SpO 2 $\leq$ 93% on room air), diarrhea (presence/absence), and age ( $<$ 65/ $\geq$ 65). Each subject will be treated for 7 consecutive days. Additionally, every subject will be followed up for safety and efficacy up to day 60 (+2 days) after first dose.
	The study consists of 2 parts:
	Study Part 1: It includes 60 subjects randomized in 1:1 ratio to receive ANA001 or matching placebo to assess the safety and tolerability of ANA001 1,000 mg BID for 7 days. An independent Data Monitoring Committee will review the safety profile of ANA001 1,000 mg PO BID prior to the initiation of Part 2 of the study.  Study Part 2: It includes 376 subjects randomized in 1:1 ratio to receive ANA001 or matching placebo to demonstrate the statistical superiority of ANA001 1,000 mg PO BID for 7 days compared with matching placebo in the treatment of
	subjects with moderate and severe COVID-19. Additionally, the safety profile of ANA001 will be assessed compared with placebo.
Rationale	Niclosamide has demonstrated both antiviral and immunomodulatory activity with possible beneficial downstream effects on coagulation abnormalities observed in COVID-19. These effects support the development of ANA001, an oral formulation of niclosamide, for the treatment of COVID-19.  Hypothesis: ANA001 will reduce viral load and inflammation associated with cytokine dysregulation, acute respiratory distress syndrome (ARDS), and
	coagulation abnormalities and thus improve time to clinical improvement defined as hospital discharge recorded using the WHO Ordinal Scale for Clinical Improvement (Appendix 1).
Target Population	Patients with moderate and severe COVID-19 who fulfill the study entry criteria
Number of Participants	Total: Approximately 436 participants
	Part 1 (60 participants): 30 ANA001 + 30 matching placebo

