#### 6.6.1.3 Replacement of Participants

Randomized participants may not be replaced.

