# 6.6.2 Discontinuation or Termination of the Study

An independent Data Monitoring Committee (DMC) will be formed and constituted according to appropriate regulatory agency guidelines. Detailed information regarding the composition of the committee and detailed procedures will be provided in a separate DMC charter. The independent DMC will review the safety, tolerability, and efficacy data of Study Part 1 and Study Part 2 as described in the DMC charter.

An emergency DMC meeting will convene if 3 or more blinded participants in Study Part 1 or 10 or more blinded participants in Study Part 2 experience AEs leading to premature discontinuation of study drug.

The Sponsor may discontinue further enrollment of the study at any time (including after unblinding of Study Part 1 study data and before enrollment of Study Part 2).

Additionally, the Sponsor may (before beginning enrollment of Study Part 2):

- Exclude a specific patient subgroup due to potential safety concerns
- Modify allowed concomitant medication due to potential safety concerns, OR
- Modify other protocol criteria due to potential safety concerns (e.g., safety laboratory monitoring or PK sampling)
- Modify the sample size and/or endpoints of Study Part 2 if Study Part 1 efficacy data suggests that such changes may be necessary to adequately power Study Part 2

The DMC may also recommend interruption of recruitment at ANY time during Study Part 1 or Study Part 2 for further analysis. The DMC may also recommend termination of the study if any one of the following are observed and not associated with the natural course of COVID-19 (based on CTCAE v5:

https://ctep.cancer.gov/protocoldevelopment/electronic\_applications/docs/CTCAE\_v5\_Quick Reference 5x7.pdf):

- Grade 4 or greater nausea, vomiting, diarrhea, or abdominal pain lasting >72 hours in participants who have received maximal medical care
- Grade 4 or greater anemia, neutropenia, or thrombocytopenia without an alternative etiology

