7.4. Efficacy Analysis for Secondary Endpoint

The secondary efficacy endpoint for Part 1 of this study is the median time (in hours) from randomization to hospital discharge (where discharge is defined as a score of 1 or 2 in the WHO Ordinal Scale for Clinical Improvement).

Kaplan-Meier curves will be constructed to display time-to- hospital discharge. Participants who are lost to follow-up or ended study early prior to achieving clinical improvement will be censored at the day of the last obtained assessment of their WHO Ordinal Scale for Clinical Improvement. Participants who complete follow-up without hospital discharge will be censored at the day of their Day 60 visit. Participants who die for any reason during the study will be right-censored at Day 60 or date of death, whichever is earlier. For the analysis of this efficacy endpoint, missing scores of the WHO Ordinal Scale for Clinical Improvement will be assumed to be > 2 (*i.e.*, no hospital discharge). Median time-to-clinical improvement and corresponding 95% confidence interval will be estimated from the Kaplan-Meier curves and tabulated for each treatment group.

The Cox proportional hazard method will be used to calculate the hospital discharge rate ratio of ANA001 relative to placebo while controlling for the stratification factors, baseline WHO Ordinal Scale for Clinical Improvement, and number of co-existing conditions. Hospital discharge rate ratio is akin to a hazard ratio but for the beneficial outcome of hospital discharge.

A hospital discharge rate ratio > 1 indicates a benefit for ANA001. Treatment groups will be compared using a stratified log-rank test.

The above analyses will be produced for all participants in the Full Analysis Set and by baseline WHO Ordinal Scale for Clinical Improvement scores. Additionally, the same analysis will be produced for participants in the Per-Protocol Analysis Set and Safety Analysis Set.

If WHO Ordinal Scale are missing at baseline, 6 hours window after first dose will be added for baseline values.

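### Part 2's 376 subjects are not expected to give the 374 recoveries behind its 85% power, and no allowance for deaths or losses is stated

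*Protocol*

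**What the plan says.** Protocol Section 9.1.2 sizes Part 2 in two steps.

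- **Events.** The section expects that "subjects treated with placebo will have a median time to clinical improvement around 15 days" and that ANA001 shortens this to 11 days. It concludes: "At least 374 recoveries must be achieved for a log rank test to have 85% power at a two-sided significance level of 0.05".
- **Subjects.** "Assuming a 6 months accrual period and the last enrolled subject will be followed for 30 days, at least 376 subjects must be randomized", that is, 188 per arm.

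Other places bear on the second step:

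- The Synopsis (Study Design) says that "every subject will be followed up for safety and efficacy up to day 60".
- Section 6.6.1.3: "Randomized participants may not be replaced".
- SAP Section 7.4, written for Part 1 but for the same time-to-discharge endpoint: "Participants who complete follow-up without hospital discharge will be censored at the day of their Day 60 visit". It also right-censors deaths, so a death never counts as a recovery.

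Section 9.1.2 names no survival distribution and no rate of death, withdrawal or loss to follow-up.

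**The concern.** Requiring 374 recoveries from 376 subjects means that 99.5% of those randomized must be seen to leave hospital (374/376 = 0.9947). With a placebo median of 15 days and follow-up ending at Day 60, some subjects would still be in hospital at the end even if nobody died or was lost. The section also assumes 30 days of follow-up for the last subject, while the rest of the protocol follows everyone to Day 60.

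At stake is the power statement for the Part 2 primary efficacy endpoint. If the stated N does not deliver the stated event count, 85% is overstated. With no margin, each death or loss before discharge reduces the expected count further. A reader also cannot tell which follow-up rule or attrition assumption produced 376.

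**Working it through.** **Inputs from Protocol 9.1.2:** medians of 15 days (placebo) and 11 days (ANA001); two-sided 0.05; 85% power; 1:1 allocation; N = 376; 6 months' accrual; last subject followed 30 days. **From the Synopsis:** every subject followed to Day 60. **Assumed here:** exponential times to discharge, uniform accrual over 182.5 days, and no deaths or losses until step 5.

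**1. The plan's event count.** The rate ratio is 15/11 = 1.364. By Schoenfeld's formula,

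events = 4(1.960 + 1.036)² / [ln(15/11)]² = 373.3, rounded up to 374.

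This matches the protocol exactly and supports the exponential reading, because under that model the ratio of medians is the rate ratio. Freedman's formula would give 380.

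**2. Expected recoveries.** The rates are λ = ln2/15 = 0.0462 per day (placebo) and ln2/11 = 0.0630 per day (ANA001).

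- Fixed follow-up T: p = 1 − exp(−λT).
- Accrual period A and a common cut-off F days after last entry: p = 1 − [exp(−λF) − exp(−λ(F+A))]/(λA).
- Expected recoveries are 188 × (p placebo + p ANA001). N for 374 is 374 divided by the mean p. Power is Φ(√events × ln(15/11)/2 − 1.960).

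| Follow-up rule | p placebo / ANA001 | Recoveries from 376 | Power | N for 374 |
|---|---|---|---|---|
| Cut-off 30 days after last entry (9.1.2 inputs) | 0.9704 / 0.9869 | 368.0 | 84.5% | 383 |
| Every subject to Day 60 | 0.9375 / 0.9772 | 360.0 | 83.7% | 391 |
| Every subject to Day 62 (end of visit window) | 0.943 / 0.980 | 361.5 | 83.9% | 389 |
| Cut-off 60 days after last entry | 0.9926 / 0.9980 | 374.2 | 85.1% | 376 |

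Reading the 30 days as the follow-up of each subject would be much worse (301 recoveries, 76.7% power). The conclusion does not rely on that reading.

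**3. Still undischarged at Day 60.** Placebo: 188 × 0.0625 = 11.75. ANA001: 188 × 0.0228 = 4.29. That is about 16 subjects, against the 2 that 374 of 376 allows.

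**4. Where 376 may come from.** Only the last row reproduces it (374/0.9953 = 375.8), so the 30 days may be a slip for 60. That row lets early entrants contribute events until the study closes. About 374.2 − 360.0 ≈ 14 of its recoveries fall after Day 60, beyond the follow-up provided.

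**5. Attrition, at illustrative rates (the documents give none).**

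- Losing 5% or 10% of the 360 expected recoveries leaves 342 or 324, with power 81.8% or 79.7%.
- Losing 5% or 10% of subjects before discharge by Day 60 leaves 344 or 327, with power 82.0% or 80.1%.

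**6. Simulation check** (20,000 log-rank trials per setting, standard error about 0.26 points):

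- 30-day cut-off: 368.0 events, power 84.2%.
- Day 60: 359.9 events, power 83.9%.
- 60-day cut-off: 374.2 events, power 84.5%.
- 5% or 10% of subjects lost: 343.7 or 327.4 events, power 82.2% or 79.9%.

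**The case against.** The strongest reply is that the gap is smaller than the precision of the inputs. The placebo median is given only as around 15 days. With 15.1 days the same formula needs 358 recoveries, fewer than the 360 expected by Day 60. In the simulation the Day 60 rule falls only 0.6 points below the cut-off that delivers 374 events, and the 30-day rule only 0.3 points below it. The 82% and 80% figures depend on loss rates that the documents do not give. This stands as a limit on size: before attrition the loss of power is minor.

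The exponential model is inferred, and the result is sensitive to it. With the same medians and Day 60 follow-up, a Weibull shape of 1.1 needs about 309 events and expects 366 (power about 90%). A shape of 0.9 needs about 461 and expects 351 (about 74%). This also stands. However, 374 is the exponential answer, so the step from 374 to 376 has to be judged under that model.

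It can also be said that the plan can be corrected later. Section 6.6.2 lets the sponsor "Modify the sample size and/or endpoints of Study Part 2 if Study Part 1 efficacy data suggests that such changes may be necessary", Section 9.4 defers detail to the SAPs, and Section 9.6 plans multiple imputation. The SAP supplied covers Part 1 only, so its censoring rule is indirect evidence for Part 2. None of this repairs Section 9.1.2. The Synopsis sets Day 60 independently of the SAP, Section 9.1.2 states no rule to continue until 374 recoveries, and imputation supplies no attrition rate and cannot make a death a recovery.

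**Conclusion.** The concern holds. The 374 recoveries are correctly derived, but 376 subjects are not expected to deliver them under either follow-up rule the protocol states. The shortfall is about 6 recoveries on the section's own inputs and about 14 with Day 60 follow-up, or 0.5 and 1.3 power points against 85%. The only rule that reproduces 376 needs follow-up past Day 60 and still allows for no deaths or losses.

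The practical weight lies in the missing margin. In hospitalized patients with moderate or severe COVID-19, some deaths and losses before discharge must be expected, and plausible rates put power nearer 80% to 82%. Those rates are assumptions, and all the figures rest on exponential discharge times. This should be fixed because a stated count and power do not follow from the stated design, but it is not a serious under-sizing.

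**What to change.** Keep N at 376, adopt Day 60 as the single follow-up rule, and rewrite Section 9.1.2 along these lines:

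> With 374 recoveries, the two-sided 5% log-rank comparison would have 85% power. Part 2 will randomize 376 subjects, 188 per arm. Assuming exponential times to discharge (medians 15 and 11 days) and follow-up of each subject to Day 60, about 360 recoveries and about 84% power are expected before deaths and losses. If a further x% of these recoveries are lost to death or dropout [rate and its basis to be supplied by the sponsor], power is lower: for illustration, 5% gives about 342 recoveries and 82%, and 10% gives about 324 and 80%.

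With a fixed Day 60 horizon the accrual period no longer enters the calculation and can be dropped.

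The cost is wording only. N and the total of 436 are unchanged, and the stated power before attrition falls by about one point. If the sponsor wants a true 85%, it needs 391 subjects before attrition, or about 412 or 435 if 5% or 10% of expected recoveries are lost. Section 6.6.2 already provides for changing the Part 2 sample size before Part 2 enrollment, although it ties this to the Part 1 efficacy data.
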